### Secondary:

- Per patient: concordance in cases, concordance in controls, sensitivity, specificity, positive predicted value, negative predictive value
- Per lesion: distribution of lesions seen on each modality
- Proportion of diagnostic quality scans using the faster protocol compared to first cohort of 80 participants

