In another 30 patients we have shown superior evaluation of skeletal disease extent with the combined  $^{18}\text{F}$  NaF/ $^{18}\text{F}$  FDG PET/CT and the WBMRI compared to  $^{99\text{m}}\text{Tc}$ -MDP scintigraphy. Further, PET/CT and WBMRI detected extra-skeletal disease that may change the management of these patients. A combination of  $^{18}\text{F}$  NaF/ $^{18}\text{F}$  FDG PET and WBMRI may provide the most accurate staging of patients with breast and prostate cancers.

The recent introduction of hybrid PET/MRI scanners in clinical practice showed promising initial results for several clinical scenarios. More than a decade ago, multimodality imaging was introduced into clinical routine with the development of the PET/CT. Since then, PET/CT has been widely accepted in clinical imaging and has emerged as one of the main cancer imaging modalities. With the recent development of combined PET/MRI systems for clinical use, a promising new hybrid imaging modality is now becoming increasingly available. The combination of functional information delivered by PET with the morphologic and functional imaging of MR imaging (e.g., diffusion-weighted imaging, dynamic contrast-enhanced MR imaging and MR spectroscopy) offers exciting possibilities for clinical applications as well as basic research. However, the differences between CT and MR imaging are fundamental. This also leads to distinct differences between PET/CT and PET/MRI not only regarding image interpretation but also concerning data acquisition, data processing and image reconstruction. PET/MRI is expected to show advantages over PET/CT in clinical applications in which MRI is known to be superior to CT due to its high intrinsic soft tissue contrast. Two of these clinical indications are breast and prostate cancers.

80 subjects were enrolled to compare  $^{18}\text{F}$  NaF/ $^{18}\text{F}$  FDG PET/MRI and the to  $^{99\text{m}}\text{Tc}$ -MDP scintigraphy. Our results indicate that the ability of  $^{18}\text{F}$  NaF/ $^{18}\text{F}$  FDG PET/MRI to identify more skeletal lesions than  $^{99\text{m}}\text{Tc}$ -MDP BS, and to additionally

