## 2.4 Study Design

We intend to perform a prospective trial to determine the role of the combined  $^{18}\text{F}$  NaF/ $^{18}\text{F}$  FDG PET/MRI in the evaluation of skeletal metastases in patients with breast and prostate cancers. This study will be a comparative study that will investigate different types of bone scanning techniques. Patients will undergo preliminary evaluations to ensure eligibility, receive and sign informed consent, be enrolled in the trial, and then undergo the combined  $^{18}\text{F}$  NaF/ $^{18}\text{F}$  FDG PET/MRI. Patients will be followed clinically by 12-months post scan evaluation.

Patients who present to the Nuclear Medicine and Molecular Imaging Clinic for a  $^{99\text{m}}\text{Tc}$  MDP bone scan as part of their routine disease work-up/standard of care will be asked to participate in this study. If agreeable, written informed consent will be obtained by a member of the research team after explaining the risks, benefits, and procedures of the study. We will follow Stanford guidelines for screening patients for renal function prior to PETMRI if they are getting contrast. All scans will be performed within a 1-month timeframe. Blind interpretation of the combined  $^{18}\text{F}$  NaF/ $^{18}\text{F}$  FDG PET/MRI will be performed by Nuclear Medicine and Radiology readers. A direct comparison for each detected lesion will be performed among the imaging modalities.

We will attempt to recruit patients who are referred for a  $^{99\text{m}}\text{Tc}$  MDP bone scan for detection of skeletal metastases. In a typical year, approximately 3,500  $^{99\text{m}}\text{Tc}$  bone scans are performed in our Clinic, 90% (3,150) of them with referral for osseous metastases identification. We plan to recruit 40 patients per year for 2 consecutive years. Cancers with highest potential to metastasize to the skeleton (breast and prostate cancers) will be considered.

All age ranges of adult population (>18-year-old) will be recruited. Both men and women will be recruited. All ethnic background will be recruited. No healthy volunteers will be recruited. Pregnant women will be excluded because of the risk posed by unnecessary radiation to the fetus. Patients with metallic implants (prosthesis, ICD, pacemakers) will be excluded since these are contraindications for MRI.

The subjects will be paid \$150 to participate in this protocol. No costs will be charged to the subjects.

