#### **5.3 Details of processing/analysis**

The PET/MRI scans will be interpreted by 2 ABNM certified Nuclear Medicine physicians ([name], [name]) and 2 ABR certified Radiologists ([name], [name]) with significant clinical experience, blinded to the subjects' medical history and the results of other imaging modalities. The outcomes of the imaging methods will be analyzed and compared against each other. Consensus read will be obtained for each scan. Characterization of lesions as true positive, true negative, false positive or false negative will be done through a combination of clinical follow up, imaging follow-up and/or histopathology findings (when possible). For purposes of this study, the investigators will document an overall diagnosis of the findings for each scan on a 5 point scale to permit a receiver operating characteristic (ROC) analysis (1=benign, 2=likely benign, 3=uncertain, 4=likely malignant, 5=malignant). If the diagnosis is positive for metastases on any of the scans, the investigator will identify the number of lesions and locations of positivity, and record this information.

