## 10.2 Key Variables

Diagnostic bone metastases status using  $^{99\text{m}}\text{Tc}$  MDP bone scan,  $^{18}\text{F}$  NaF/ $^{18}\text{F}$  FDG PET/MRI, bone metastases status at 12 months (all binary)

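### The secondary per-lesion endpoint does not use the true/false lesion status assigned in Section 5.3, so it cannot tell better detection from extra false-positive lesions

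*Combined protocol and SAP*

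**What the plan says.** Section 10.3 lists the secondary endpoints. At patient level they are "Per patient: concordance in cases, concordance in controls, sensitivity, specificity, positive predicted value, negative predictive value". At lesion level the whole definition is "Per lesion: distribution of lesions seen on each modality".

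Section 5.3 plans a reference status for lesions: "Characterization of lesions as true positive, true negative, false positive or false negative will be done", based on the later clinical course, later imaging, or tissue where it can be obtained. It also says that, when any scan is read as positive, "the investigator will identify the number of lesions and locations of positivity, and record this information".

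Section 2.4 adds "A direct comparison for each detected lesion will be performed among the imaging modalities", which compares modality with modality and not with the reference.

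Section 10.2 names the variables for analysis: metastasis status by each modality and "bone metastases status at 12 months (all binary"). Section 10.4 has secondary endpoints calculated pooled and by disease, and gives no method for lesions.

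Section 2.3, reporting on the 80 patients already enrolled, counts the ability of PET/MRI "to identify more skeletal lesions than" bone scanning, together with its detection of disease outside the skeleton, as a benefit.

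**The concern.** A lesion seen on a scan is either a metastasis or something else. A modality that marks more lesions may be finding more disease, calling more benign uptake malignant, or both. The protocol plans to establish which, but the endpoint that describes lesions does not ask for the result. A reader given only the distribution by modality would have to guess.

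The likely guess is that more is better, because Section 2.3 already presents a higher skeletal lesion yield as part of the advantage of PET/MRI. At stake is how a descriptive secondary result is interpreted: the lesion table could look favourable to a modality that is no more sensitive than bone scanning, or even less so.

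**Working it through.** **1. Follow the lesion status through the plan.**

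- Section 5.3 creates it: true or false, positive or negative, for lesions.
- Section 10.1 requires a 12-month bone evaluation for a patient to be analysed.
- Section 10.2 carries this forward as a binary metastasis status and lists no lesion-level reference variable.
- Section 10.3 attaches sensitivity, specificity and predictive values to the patient. The lesion line mentions no reference.
- Section 10.4 does not link lesions to their reference status.

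So the status is planned in 5.3 and not used at lesion level in 10.2 to 10.4.

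**2. Ask whether the per-patient measures fill the gap.** Each patient contributes one binary result per modality and one binary status at 12 months.

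- Patient without metastases: a false lesion that makes the scan positive is a false-positive patient. It lowers specificity and positive predictive value, so over-calling is visible here.
- Patient with metastases whose scan is already positive: the patient is a true positive whether the scan shows no false lesions or many. Sensitivity, specificity and both predictive values stay the same, so over-calling is invisible here.

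Only a lesion-level split shows the second case.

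**3. Illustrate direction and size.** The plan states no figure for this endpoint, so there is none to reproduce. Every input below is assumed: 100 true lesions, and an old modality that shows 80 of them plus 10 false ones.

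Formulas: lesions seen = 100 × sensitivity + false lesions; ratio = seen by new / seen by old; share true = true lesions seen / all seen.

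Old modality: 80 + 10 = 90 seen; share true 80/90 = 88.9%.

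| New modality: sensitivity | False lesions | Lesions seen | Ratio to old | Share true |
|---|---|---|---|---|
| 80% (unchanged) | 10 | 80 + 10 = 90 | 90/90 = 1.00 | 80/90 = 88.9% |
| 80% (unchanged) | 30 | 80 + 30 = 110 | 110/90 = 1.22 | 80/110 = 72.7% |
| 80% (unchanged) | 50 | 80 + 50 = 130 | 130/90 = 1.44 | 80/130 = 61.5% |
| 75% (worse) | 40 | 75 + 40 = 115 | 115/90 = 1.28 | 75/115 = 65.2% |
| 90% (better) | 10 | 90 + 10 = 100 | 100/90 = 1.11 | 90/100 = 90.0% |

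The less sensitive modality shows 28% more lesions than the old one, and the more sensitive one only 11% more. Ranking by lesions seen puts them in the wrong order. The split into true and false separates all five rows.

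**The case against.** The strongest reply is that the endpoint is secondary and descriptive, with no hypothesis, direction, test or decision rule. That stands. A reader might infer that the lesion endpoint supports the primary claim of better accuracy than bone scanning; the documents do not support that. The primary endpoint is per-patient concordance, Section 10.4 makes the principal analysis per patient with a kappa coefficient, and the sample-size reasoning in 10.5 and the Appendix concerns sensitivity.

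Second, a distribution need not be a pooled total. Section 2.4 plans a comparison for each lesion, and 5.3 records locations as well as numbers. This also stands: the plan does not prescribe a raw count, so it would be wrong to say that a few patients with many lesions must dominate it. But matching lesions between modalities still does not say which are real.

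Third, 10.3 could be read together with 5.3, which makes this a missing link. That is fair as to intent. As written, however, the lesion table can be produced in full compliance without reference status.

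Fourth, a reader might infer from Section 2.3 that the lesions in the first 80 patients were over-called. The documents do not show this. They do not say whether those lesions were verified, and the stated benefit also rests on extra-skeletal findings.

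Fifth, within-patient clustering matters only if intervals are given, and the plan specifies none here. With an assumed 5 lesions per patient and an assumed within-patient correlation of 0.5, the design effect would be 1 + (5 − 1) × 0.5 = 3, and naive intervals would be too narrow by a factor of √3 = 1.73. That is a caution for any added interval, not a fault in the present plan.

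Finally, verification will be incomplete. Tissue is obtained only where possible, and the Study Calendar lists one 12-month follow-up with no protocol imaging at that visit. This limits what the fix can deliver and must be shown openly.

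**Conclusion.** The point holds as a gap in a secondary, descriptive endpoint. The plan intends to class lesions as true or false but does not use that status where lesions are reported, and the per-patient measures cannot show extra false lesions in a patient who truly has metastases. The conclusion follows from the text of 5.3 and 10.2 to 10.4 and needs no numerical assumption.

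The size is not known. On the assumed counts, false lesions alone raise the number seen by 22% to 44% with no gain in sensitivity, while a real gain of 10 percentage points raises it by 11%. These figures show direction only and are not estimates for this trial. The primary endpoint and principal analysis are not affected.

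**What to change.** Redefine the per-lesion endpoint in 10.3, and add a matching sentence to 10.4, as follows:

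- Match lesions by location, and class each as seen on both modalities, on PET/MRI only, or on bone scan only.
- Cross-tabulate these against the Section 5.3 reference status: true metastasis, false positive, or unverified.
- For each modality, report the proportion of seen lesions confirmed true and the number of false-positive lesions per patient.
- State how many lesions are unverified in each cell.
- State that a higher lesion count alone will not be interpreted as better detection.
- If intervals are reported, compute them with the patient as the unit, for example by a cluster bootstrap.

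Add lesion-level reference status to the key variables in 10.2.

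The cost is a change of wording, a lesion-matching step with a rule for assigning status, and one extra table. Location and reference status are already planned in 5.3. The downside is that some lesions will remain unverified, so the proportion confirmed true will be incomplete and should be read alongside the unverified count.

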### 1.2. **Secondary Objectives**

- Evaluating the combined  $^{18}\text{F NaF}/^{18}\text{F FDG PET/MRI}$  as a reliable bone scanning modality
- Evaluating the performance and reliability of the proposed WBMRI sequences: IDEAL and eDWI
- Evaluating a fast MRI protocol (2:30 min/bed)

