identify extra-skeletal disease, represents a beneficial alternative to the single modalities performed separately.  $^{18}\text{F}$  NaF/ $^{18}\text{F}$  FDG PET/MRI is a promising approach for evaluation of skeletal and extra-skeletal lesions in a selected population of breast and prostate cancer patients. However, the current duration of exam (4 min/bed) is too long for some of the elderly patients. Therefore, we are now shortening the WBMRI protocol from 4 min/bed to 2:30 min/bed, reducing the total time from approximately 45 min/scan to 20-25 min/scan. We plan to enroll and have funding 50 additional subjects (25/year) to further evaluate the combined  $^{18}\text{F}$  NaF/ $^{18}\text{F}$  FDG PET/MRI as a reliable bone scanning modality.

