**7. STUDY CALENDAR**

	Pre-Study	Wk 1	Wk 2	Wk 3	Wk 4	12 Months
Imaging scans done within 1 month of each other		----->				
Informed consent	X					
Demographics	X					
Medical history	X					
Post-Scan Follow up						X

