## 10.4 Plan of Analysis

The principal analysis will aggregate patients from the two groups and will be conducted on a per-patient basis. We will calculate the concordance between the modalities across outcomes (combining cases and controls) and evaluate the results by calculating the kappa coefficient. Secondary endpoints will be calculated, both as aggregates of the three diseases and separately by disease. Sensitivities and other summaries will only be calculated if they involve a denominator of at least 10.

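### The fast-protocol endpoint compares 50 new patients with an earlier cohort of 80 without age adjustment, so a shift in age mix could mimic or hide a protocol effect

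*Combined protocol and SAP*

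**What the plan says.** Section 1.2 lists as a secondary objective "Evaluating a fast MRI protocol (2:30 min/bed)". The only endpoint that names this protocol is in section 10.3, among the secondary endpoints: "Proportion of diagnostic quality scans using the faster protocol compared to first cohort of 80 participants".

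Section 2.3 gives the sequence. First, "80 subjects were enrolled to compare" PET/MRI with the bone scan, and their results are already summarised there. Then: "We plan to enroll and have funding 50 additional subjects (25/year)". These 50 are scanned at 2:30 min/bed. The stated reason for the change is that "the current duration of exam (4 min/bed) is too long for some of the elderly patients", and the expected gain is "reducing the total time from approximately 45 min/scan to 20-25 min/scan".

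Section 10.4 has one rule that reaches this endpoint: "Secondary endpoints will be calculated, both as aggregates of the three diseases and separately by disease". It names no test, interval or covariate for the comparison of cohorts. Section 10.2 lists neither age nor scan quality as a key variable. The section 7 calendar has a pre-study row for "Demographics", and section 3.1 requires age to be known when the tracer is given.

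**The concern.** The comparison is before-and-after. Whatever differs between the 80 and the 50 besides minutes per bed enters the difference in proportions. Age is not a generic worry here, because the sponsor's own reason for shortening the exam is that some elderly patients find it too long. Poor tolerance is a plausible route to motion, an incomplete scan and a non-diagnostic result. A shorter exam may also change who agrees to take part, so the new protocol could itself shift the factor most likely to affect its endpoint.

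If the 50 are older than the 80, a real benefit could be hidden or reversed. If they are younger, the fast protocol could look better than it is. The section 1.2 objective has no other endpoint of its own to fall back on.

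**Working it through.** **No figure to reproduce.** The documents state no expected quality rate, difference, margin or power for this endpoint. The Appendix sample sizes concern paired sensitivity, not this comparison.

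**Inputs.** From the documents: cohort sizes 80 and 50. Assumed, for illustration only: under the old protocol, diagnostic quality is 95% in younger and 80% in older patients; older patients are 25% of the 80 and 40% or 50% of the 50.

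**1. No protocol effect.** Expected proportion = (younger share × 0.95) + (older share × 0.80).
- First 80: 0.75 × 0.95 + 0.25 × 0.80 = 0.9125
- New 50, 40% older: 0.60 × 0.95 + 0.40 × 0.80 = 0.890, crude difference −2.25 points
- New 50, 50% older: 0.50 × 0.95 + 0.50 × 0.80 = 0.875, crude difference −3.75 points

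The true difference is zero in both cases.

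**2. Real benefit in older patients only (80% to 90%), new cohort 50% older.**
- New 50: 0.50 × 0.95 + 0.50 × 0.90 = 0.925, crude difference +1.25 points
- Standardised to the first cohort's mix: (0.75 × 0.95 + 0.25 × 0.90) − 0.9125 = 0.9375 − 0.9125 = +2.5 points
- Standardised to the new cohort's mix: 0.925 − 0.875 = +5.0 points

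**3. Against sampling error.** Half-width = 1.96 × √[p₁(1−p₁)/80 + p₂(1−p₂)/50].

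| Scenario | p₁ | p₂ | Crude difference (points) | 95% half-width (points) |
|---|---|---|---|---|
| No effect, 40% older | 0.9125 | 0.890 | −2.25 | 10.7 |
| No effect, 50% older | 0.9125 | 0.875 | −3.75 | 11.1 |
| Benefit in older, 50% older | 0.9125 | 0.925 | +1.25 | 9.6 |

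**4. Wider range.** With no protocol effect, bias = (older share in the 80 − older share in the 50) × (younger rate − older rate). Take rate pairs from 95%/90% to 98%/70%, and older shares of 50% vs 40%, 50% vs 30%, 60% vs 30% and 40% vs 60%. The absolute bias then runs from 0.1 × 0.05 = 0.5 points to 0.3 × 0.28 = 8.4 points, and it is negative when the new cohort is older. One case within this range has rates of 95%/75% and shares of 60% vs 30%. It gives 83% vs 89%, a false gain of 6 points, and a 14% chance of a significant result favouring the fast protocol against a nominal 2.5%.

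**5. How much adjustment the data can bear.** Expected non-diagnostic scans:
- First 80: 80 × 0.0875 = 7
- New 50: 50 × 0.110 = 5.5, 50 × 0.125 = 6.25 or 50 × 0.075 = 3.75

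The total is about 11 to 13 of 130.

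**6. Adjusted estimators differ.** In the step 2 scenario the older stratum has 20 and 25 patients and the younger 60 and 25.
- Mantel-Haenszel weights n₁n₂/(n₁+n₂): 20 × 25/45 = 11.1 and 60 × 25/85 = 17.6. Risk difference = (11.1 × 0.10 + 17.6 × 0)/28.8 = 3.9 points.
- Standardised to the combined cohort: (45/130) × 0.10 = 3.5 points.

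The method therefore has to be fixed in advance.

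**The case against.** **Age as the cause of failed scans.** A reader might infer that the protocol names age as the reason scans fail. It does not. Section 2.3 is about exam length and tolerance. It reports no non-diagnostic scan, no failure rate and no relation between age and image quality. The step from tolerance to quality is plausible but is an inference.

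**Bias as a fact.** A reader might also conclude that the comparison is biased. The documents give no ages for either cohort, so a shift is only possible. That the difference will be crude is likewise read from the plan's silence on method.

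**Eligibility.** Section 3.1 still requires patients to keep still for about an hour, although scan time falls to 20 to 25 minutes. This may limit both a change in who enrols and the effect of age. The criteria applied to the first 80 are not given separately, so how far it does so cannot be judged.

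**Noise.** The bias in steps 1 and 2 is well inside the half-width, and +1.3, +2.5 and +5.0 points could not be told apart in one trial of this size. That is correct. But the interval describes random error only, and the plan states no interval at all.

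**Other gaps.** By-disease results are already planned, which partly covers disease mix. Diagnostic quality has no definition or named rater. The section 10.1 subset requires interpretable scans and, if applied here, would remove the failures being counted. Age adjustment cures neither of these, and neither makes it unnecessary.

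**Conclusion.** The point holds as a risk, not a demonstrated bias. The only endpoint specific to the fast protocol is a sequential, non-randomised comparison, and no adjustment is planned for the one patient characteristic that the protocol itself links to tolerating the exam. Size and direction are unknown. On the main illustrative inputs the bias is 2.3 to 3.8 points against a half-width of about 10.7 to 11.1 points; over the wider assumed range it is 0.5 to 8.4 points. All of these rest on assumed rates and age shares. The change is worth making because it is cheap and concerns a baseline value that should already be known. It affects a secondary endpoint and leaves the principal concordance analysis untouched.

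**What to change.** Add to section 10.4:
- Tabulate age by cohort.
- Report the difference in the proportion of diagnostic-quality scans, the 50 against the first 80, with a 95% CI, both crude and age-adjusted.
- Use one pre-specified adjusted method, for example a Mantel-Haenszel risk difference over two age bands fixed before the data are examined.
- Keep disease as the separate summary already planned, and do not cross it with age.
- Label the comparison descriptive.

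**Cost.** One or two sentences and a little analysis. No new data collection appears to be needed, but the documents do not describe the first cohort's dataset, so the sponsor should confirm that age is on file for all 80. The adjusted interval may be slightly wider. In the step 2 scenario the Mantel-Haenszel half-width is 1.96 × √[(11.1/28.8)² × (0.16/20 + 0.09/25) + (17.6/28.8)² × (0.0475/60 + 0.0475/25)] = 10.3 points, against 9.6 crude. With about 11 to 13 non-diagnostic scans expected on the assumed rates, adjustment cannot go much beyond one factor, so other differences between the cohorts will remain uncontrolled.

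### The fast-protocol endpoint compares scan quality across two periods with no quality item in the read and no common, masked rating, so any shift in rating standard could not be separated from the effect of shortening the scan

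*Combined protocol and SAP*

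**What the plan says.** - **Objective.** Section 1.2 lists, among the secondary objectives, "Evaluating a fast MRI protocol (2:30 min/bed").
- **Endpoint.** The last secondary endpoint in 10.3 is "Proportion of diagnostic quality scans using the faster protocol compared to first cohort of 80 participants". Diagnostic quality is not defined there or elsewhere.
- **The two cohorts.** Section 2.3 reports that "80 subjects were enrolled to compare" PET/MRI with the bone scan, summarises their results, and finds the 4 min/bed exam too long for some elderly patients. It continues: "Therefore, we are now shortening the WBMRI protocol from 4 min/bed to 2:30 min/bed". The new cohort follows: "We plan to enroll and have funding 50 additional subjects (25/year").
- **The read.** Under 5.3, two nuclear medicine physicians and two radiologists interpret the PET/MRI scans, with a consensus read for each. They are "blinded to the subjects' medical history and the results of other imaging modalities". What is recorded: "the investigators will document an overall diagnosis of the findings for each scan on a 5 point scale", running from benign to malignant, plus the number and location of lesions when a scan is positive.
- **Variables and analysis.** The key variables in 10.2 are three binary metastasis-status items. Section 10.1 limits the analysis subset to patients with interpretable scans and a known 12-month bone evaluation; interpretable is not defined. Section 10.4 pools the two groups for the principal analysis and says secondary endpoints will be calculated, overall and by disease. It gives no method for comparing one cohort with the other.

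**The concern.** The comparison is between an earlier cohort scanned one way and a later cohort scanned another way. Bed time and calendar period change together. For the difference in proportions to say something about bed time, the judgement of what counts as diagnostic must at least be the same for both sets of images. The plan does not secure this: it has no quality scale, no cut, no item on the read, no masking to bed time or cohort, and no statement that the first 80 will be rated alongside the new 50.

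Three ordinary things could then move the difference without any change in the images: a different working threshold for diagnostic, growing reader experience with PET/MRI, or awareness that a scan is the shortened one. Drift towards stricter rating would make the fast protocol look worse than it is; drift towards leniency would hide a real loss. Because the principal analysis pools the groups, it does not assess the fast protocol separately. What is at stake is whether the one endpoint written for that secondary objective can be interpreted.

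**Working it through.** The plan gives no sample size, expected rate, margin or test for this endpoint, so there is no figure of its own to reproduce. The check is first textual, then illustrative.

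**1. What each section supplies for measuring diagnostic quality**

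| Needed for a like-for-like comparison | Where it would be expected | What is there |
|---|---|---|
| Definition and cut | 10.3 | None |
| Item on the read | 5.3 | 5-point diagnosis; lesion number and location |
| Variable | 10.2 | Bone scan, PET/MRI and 12-month metastasis status |
| Masking to bed time or cohort | 5.3 | Masking to history and other imaging only |
| Same readers and scale for both cohorts | 5.3, 10.3 | Not stated |
| Re-read or mixed-order read of the 80 | 5.3, 10.4 | Not stated |
| Between-cohort method | 10.4 | Not stated |

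**2. Why period and protocol cannot be separated**

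Write the observed proportion in each cohort as true quality plus a rating shift:

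observed difference (50 minus 80) = (true quality at 2:30 − true quality at 4) + (rating shift in the later period − rating shift in the earlier period).

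Each protocol is seen in one period only. The data give one number for the sum, and nothing in the plan estimates the second bracket. A change in rating standard passes one-for-one into the estimated difference.

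**3. Illustration of size**

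Inputs from the documents: n = 80 and n = 50. Assumptions: true quality 90% or 80%, identical in both cohorts; the later ratings stricter by d points; a pooled two-sided z test at 5%. The rejection probability is the sum, over all pairs (i, j), of P(i | 80, p) × P(j | 50, p − d) for those pairs where

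|i/80 − j/50| / √[p̄(1 − p̄)(1/80 + 1/50)] > 1.96, with p̄ = (i + j)/130.

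| Drift d (points) | True quality 90% | True quality 80% |
|---|---|---|
| 0 | 4.9% | 5.1% |
| 1 | 5.5% | 5.5% |
| 2 | 6.8% | 6.3% |
| 3 | 8.7% | 7.6% |
| 5 | 14.3% | 11.2% |
| 10 | 36.4% | 27.0% |
| 15 | 62.7% | 49.0% |

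Drift in the other direction masks a loss. If the true rate fell from 90% to 80% and later ratings were 10 points more lenient, the observed rates would both be 90%, and the difference would be flagged 4.9% of the time rather than 36.4%.

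**4. Comparison with sampling error**

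95% half-width = 1.96 × √[p(1 − p)(1/80 + 1/50)].

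- At 90%: 1.96 × √(0.09 × 0.0325) = 1.96 × 0.0541 = 0.106, about 11 points.
- At 80%: 1.96 × √(0.16 × 0.0325) = 1.96 × 0.0721 = 0.141, about 14 points.

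At 90%, a 10-point drift is about as large as the half-width (10/10.6 = 0.94), a 5-point drift about half of it (5/10.6 = 0.47), and 1 to 3 points well below it.

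**The case against.** The best reply is that the plan is silent rather than wrong. It does not prescribe rating the 50 as they arrive and taking the 80 from old reads, and it does not say that readers will know a scan is the fast one. A reader might infer that no quality judgement exists for the first 80. The documents do not support that: only the current text of 5.3 is available, not the forms used then, and the interpretable condition in 10.1 implies some usability judgement, though an undefined one. A reader might also infer that drift has happened. Nothing shows it, and a four-reader consensus may keep it small; at 1 to 3 points the effect in the table is minor. All of this stands, and it makes the point conditional.

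It is also fair that the probabilities belong to a test the plan does not contain. Section 10.4 only says that secondary endpoints will be calculated. Nor is there a rule for accepting or rejecting the 2:30 min/bed protocol, which 5.2 already specifies, so one cannot say that the trial would make a wrong decision on it.

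What does not stand is that consensus, or a definition alone, would settle the matter. Consensus limits variation within a read, not a shift in threshold over time, and nothing says the same readers or criteria were used for the 80. A definition applied only to the new 50 leaves the 80 judged differently. If diagnostic quality is to be determined other than by reader rating, the plan does not say so, and equal measurement is still not assured.

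**Conclusion.** The point holds as a measurement gap in a secondary, apparently descriptive endpoint. The only endpoint naming the fast protocol compares two non-concurrent cohorts on an attribute that the stated read does not record, and the plan has no provision for rating both alike. A change in rating standard, if there is one, could not be told apart from the effect of the shorter scan.

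This follows from the text and needs no assumption. Its size cannot be derived from the documents. Under the assumed 90% quality and a two-sided 5% test, the chance of a false difference rises from 4.9% to about 7%, 14% or 36% with 2, 5 or 10 points of drift, against a 95% half-width of about 11 points. The quality level, the drift sizes and the test are all assumptions. The change is worth making because it is cheap, not because bias has been shown.

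**What to change.** In 5.3 and 10.3:

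1. Define diagnostic quality by one fixed scale with a pre-stated cut, and add it to the read.
2. Have the existing 5.3 readers rate the archived images of the first 80, where retrievable, and the images of the new 50 in a single random-order series, with date, cohort and bed time removed.
3. Base the 80-versus-50 comparison on these ratings only.
4. Use all scans acquired as the denominator, not only the interpretable subset of 10.1. Otherwise non-diagnostic scans could drop out before the proportion is formed. Report how many of the 80 could not be retrieved.
5. In 10.4, describe the result as a descriptive, non-concurrent comparison and report it with a confidence interval.

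The cost is protocol wording and reader time for a quality-only rating of up to 130 scans (80 + 50); no new patients or scans are needed. Two limits remain. Masking may be imperfect if fast scans look noisier, although a common scale and session series would still take out the period shift in rating. Differences in case mix and other period effects stay confounded with bed time whatever is done about the ratings. The wording should be settled before the new scans are rated for quality.
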